5 ANALYSIS VARIABLES

Analysis variables will be required from both the UX001-CL201 study, carried over week 24 and week 48 analysis variables, as well as from UX001-CL202 from both Part I and Part II.

Additional variables may be added as this SAP is developed and/or as discussion unfolds concerning the usefulness of *derived* variables formulated using the information presented below.

5.1 Study Drug Dosing

Study Drug Dosing for the UX001-CL201 feeder study and for this study UX001-CL202 are mapped to present all possible treatment combinations that a subject may participate in within these two studies (Table 3).

Table 3 Study Drug Dosing Pathways: UX001-CL201 – UX001-CL202

Path	UX001-CL201		UX001-CL202	
	Weeks 0-24	Weeks 24-48	Part I	Part II
1	6g/day	6g/day	6g/day	12g/day
2	3g/day	3g/day	6g/day	12g/day
3	0g/day	6g/day	6g/day	12g/day
4	0g/day	3g/day	6g/day	12g/day
5	N/A	N/A	N/A	12g/day

The 0/6 and 0/3 treatment groups (pathways 3 and 4) may be combined during weeks 0-24 for UX001-CL201 subjects to form a placebo group for comparisons with pathway 5.

The 0/6 and 6/6 treatment groups (pathways 1 and 3) and 0/3 and 3/3 treatment groups (pathways 2 and 4) may be combined to form 3g and 6g treatment groups for comparison with the 12g/day SA-ER/SA-IR dosing.

A total of 5 separate treatment pathways are identified for evaluation. Subjects enrolled in UX001-CL202 who are members of the TNP will have no treatment pathway from the UX001-CL201 study. Subjects who roll over from UX001-CL201 into Part I of this study will continue on a dose of 6g/day SA-ER. These data will be used primarily for additional safety data. All subjects participating in Part II of this study will receive 12g/day SA-ER/SA-IR. The focus of the safety analyses for the primary objective will be on safety at the 6g/day SA-ER and safety at the 12g/day SA-ER/SA-IR doses.

5.2 Demographics and Baseline Characteristics

Demographic and Baseline Characteristics for the study population in UX001-CL202 will include the parameters listed in Table 4. For Subjects who roll over from the UX001-CL201 demographic parameters will be cross validated from the UX001-CL201 study into the UX001-CL202 study as the same variable.

Table 4 Demographic and Baseline Characteristic Variables

Analysis Variable Name	Analysis Variable Description	Code List/ Variable Notes
SEX	Subject Gender	M = Male, F = Female Will be carried over from UX001-CL201
AGE AGE1	Subject Age at time of Informed Consent – UX001-CL201 Subject Age at time of Informed Consent – UX001-CL202	Computed as (Date of Informed Consent – Date of Birth / 365.25) +1 For Subjects carried over from UX001-CL201 two ages will be reported: AGE and AGE1
RACE	Subject Race	1 = White, 2 = Black or African American, 3 = Asian, 4 = Native Hawaiian or Other Pacific Islander, 5 = American Indian or Alaska Native, 6 = Other (Specified). Will be carried over from UX001-CL201
ETHNIC	Subject Ethnicity	1 = Hispanic or Latino, 2 = Not Hispanic or Latino Will be carried over from UX001-CL201
HT	Subject Height at Baseline	Height in CM, assessed at baseline visit in UX001-CL202
WT	Subject Weight at Baseline	Weight in KG, assessed at baseline visit in UX001-CL202

Analysis Variable Name	Analysis Variable Description	Code List/ Variable Notes
BMI	Subject Body Mass Index (BMI) at baseline	Derived from baseline HT and Weight. Computed as WT (kg) / HT (m ²)
BMICAT	Subject BMI Category at baseline	Derived from BMI and assigned as: 1 = Underweight (<18.5) 2 = Normal weight (18.5–24.9) 3 = Overweight (25.0–29.9) 4 = Obese (30.0-39.9) 5 = Morbidly Obese (≥40.0)
Interval History	Analysis variables related to collection of HIBM interval history	Interval History data will be reported as collected by category.

5.3 Safety Variables

Safety analysis variables for the study population in UX001-CL202 will include the parameters listed in Table 5. Safety analysis variables will be summarized for Part I and Part II in this study. Baseline safety analysis variable values for subjects who roll over from UX001-CL201 will be the last safety variable assessment recorded in UX001-CL201. For subjects who are SA Naïve and enroll into Part II of this study the baseline value will be assigned as the screening visit for the subject.

Table 5 Safety Analysis Variables

Analysis Variable Name	Analysis Variable Description	Code List/ Variable Notes
Medical History: MHTERM MHDECOD MHPTCD MHBODSYS MHSOC MHSOCCD	Verbatim MH Text Preferred MH Term Preferred Term Code Body System (SOC) Primary SOC Primary SOC Code	Will be carried over from UX001-CL201 for roll over subjects SA Naïve subjects will have baseline Medical History recorded at the screening visit Medical History will be coded with MEDDRA medical dictionary SOC and Preferred term. Medical history will be

Analysis Variable Name	Analysis Variable Description	Code List/ Variable Notes
		listed for all subjects participating in UX001-CL202
Physical Examination PE TERM PEDECOD	Verbatim PE Text Preferred PE Term	Physical Examination data will be reported as collected by term.
Neurological Examination NE TERM NEDECOD	Verbatim NE Text Preferred NE Term	Neurological Examination data will be reported as collected by term.
Concomitant medications: CMTRT CMDECOD PREFCODE DCL2C	Verbatim CM Text Preferred CM Term Preferred Code ATC Level 2 Code	Concomitant Medications will be coded with WHODRUG medications dictionary to primary term and ATC Level 2 code. Concomitant Medications will be listed for all subjects participating in UX001-CL202
Adverse Events AETERM AEDECOD AEPTCD AEBODSYS AESOC AESOCCD AESEV AECTCAE	Verbatim AE Text Preferred AE Term Preferred Term Code Body System (SOC) Primary SOC Primary SOC Code AE Severity Code CTCAE Severity Grade	Adverse Events will be assessed on a continual basis during the conduct of the trial. Adverse Events will be coded with MEDDRA medical dictionary SOC and Preferred term
Vital Signs: SYSBP DIABP HR RP TEMP	Systolic BP(mmHg) Diastolic BP (mmHg) Heart Rate (bpm) Respiratory Rate (bpm) Temperature (°C)	Vital Signs will be assessed at baseline and at subsequent visits over the course of the study. Baseline will be carried over for UX001-CL201

Analysis Variable Name	Analysis Variable Description	Code List/ Variable Notes
		roll-over subjects from the last visit in UX001-CL201.
Laboratory Studies: LBCAT=HEMA HB MCHC MCHB MCV PLATLET RBC RETIC WBCDIFF NEUTABS NEUTPCT LYMPABS LYMPPT EOSINABS EOSINPCT BASOABS BASOPCT WBC	Hemoglobin (Hb) MCH Concentration Mean Corpuscular Hb Mean Corpuscular Vol Platelet Count Red Blood Cell Count Reticulocyte Count WBC Differential Neutrophil count (abs) Neutrophil count (%) Lymphocyte count (abs) Lymphocyte count (%) Eosinophil count (abs) Eosinophil count (%) Basophil count (abs) Basophil count (%) White Blood Cell	Laboratory data will be identified stored by category (LBCAT) and test code (LBTESTCD). Units standardized across the study.
Laboratory Studies: LBCAT=CHEM ALTSGPT ALKP AMY ASTSGOT BILID BILIT BUN CALC CHLOR CHOLT CK	Alanine aminotransferase Alkaline phosphatase Amylase Aspartate aminotransferase Bilirubin (direct) Bilirubin (total) Blood urea nitrogen Calcium Chloride Cholesterol (total) Creatine kinase (CK)	Laboratory data will be identified stored by category (LBCAT) and test code (LBTESTCD). Units standardized across the study.

Analysis Variable Name	Analysis Variable Description	Code List/ Variable Notes
CREAT GGT GLUC LDH LIP PHOS K ALB ALBT TRIG	Creatinine Gamma-glutamyl transpeptidase Glucose Lactate dehydrogenase Lipase Phosphorus Potassium Protein (ALB) Protein (Total) Triglycerides	
Laboratory Studies: LBCAT=URINE COLOR PH SG KET PROTEIN GLUC BILI NIT UROB HEMO CREAT	Color pH Specific Gravity Ketones Protein Glucose Bilirubin Nitrate Urobilinogen Hemoglobin Creatinine	Laboratory data will be identified stored by category (LBCAT) and test code (LBTESTCD). Units standardized across the study.
Laboratory Studies: LBCAT=SPEC FSACID PREGS PREGU	Free serum SA Serum Pregnancy Urine Pregnancy	Laboratory data will be identified stored by category (LBCAT) and test code (LBTESTCD). Units standardized across the study.

5.4 Efficacy Variables

Efficacy analysis variables for the study population in UX001-CL202 will include the parameters listed in [Table 6](#). Efficacy analysis variables will be summarized for Part II in this study to gain a better understanding of the 12 g/day SA-IR dose. Baseline efficacy analysis

variable values for subjects who roll over from UX001-CL201 will be identified based on the requested analysis. Multiple baselines will be used to evaluate the change in disease course over the treatment pathways (Table 3). The baseline value to be used for the change from baseline comparisons will be identified with the specific analyses described in this SAP.

Clinical efficacy analyses to be completed may include the following for the analysis variables listed below:

- (1) Muscle strength as measured by HHD UE, LE and individual components, and reported as force in kg and percent of predicted normal,
- (2) Walking ability as measured by the 6MWT, and reported as distance in meters and percent of predicted normal,
- (3) Walking speed as measured by the walking speed test, which will be reported in seconds and percent of predicted normal for each walking speed, comfortable and maximum,
- (4) Arm raising ability as measured by the weighted arm lift test, which will be reported as the total number of completed repetitions.
- (5) Functional disability as measured by the HIBM-FAS, which will be reported as a total score and subscale scores for mobility, self-care, and upper extremity function with lower scores associated with greater disability.

Table 6 Efficacy Analysis Variables

Analysis Variable Name	Analysis Variable Description	Code List/ Variable Notes
Hand Held Dynamometry: LELBEXT LELBFLX LGRIP LHIPABD LHIPADD LHIPEXT LHIPFLX LKEY LKNEEXT LKNEFLX LPALMAR LSHLDABD	Left Elbow Extension (kg) Left Elbow Flexion (kg) Left Grip (kg) Left Hip Abduction (kg) Left Hip Adduction Left Hip Extension (kg) Left Hip Flexion (kg) Left Key (kg) Left Knee Extension (kg) Left Knee Flexion (kg) Left Palmar (kg) Left Shoulder Abduction (kg)	Muscle strength based on the maximum voluntary isometric contraction (MVIC) against a hand-held dynamometer will be measured in the following muscle groups: gross grip, pinch, shoulder abductors, elbow flexors, elbow extensors, hip abductors, hip

Analysis Variable Name	Analysis Variable Description	Code List/ Variable Notes
LTIP RELBEXT RELBFLX RGRIP RHIPABD RHIPADD RHIPEXT RHIPFLX RKEY RKNEEXT RKNEFLX RPALMAR RSHLDABD RTIP HHDHECS HHDLECS	Left Tip (kg) Right Elbow Extension (kg) Right Elbow Flexion (kg) Right Grip (kg) Right Hip Abduction (kg) Right Hip Adduction Right Hip Extension (kg) Right Hip Flexion (kg) Right Key (kg) Right Knee Extension (kg) Right Knee Flexion (kg) Right Palmar (kg) Right Shoulder Abduction (kg) Right Tip (kg) HHD Upper Extremity CS HHD Lower Extremity CS	adductors, hip flexors, hip extensors, knee flexors and knee extensors. The total force (kg) will be measured as well as the percent of predicted normal force based on age, gender, height and weight (where applicable).
Six-Minute Walk Test: SXMWTDIS SXMWTPP	6-Min Walk Test (meters) 6-Min Walk Test (%pred)	The total distance walked (meters) in a six minute period will be measured as well as the percent of predicted normal distance based on age and gender.
Walking Speed Test: COMFWALK MAXWALK	Comfortable Gait Speed (cm/s) Maximum Walk Speed (cm/s)	The time required to walk 25 feet (7.62 meters) will be assessed at a comfortable and a maximum gait speed. The total number of seconds required for each speed will be recorded. Individual subject performance will also be compared to healthy peers based

Analysis Variable Name	Analysis Variable Description	Code List/ Variable Notes
		on normative data.
Weighted Arm Lift Test LNUMLIFT RNUMLIFT	Left Arm Number of Lifts Right Arm Number of Lifts	The number of times the subject can raise a 1 kg weight above the head in a 30-second period will be recorded. The test will be performed bilaterally.
HIBM Functional Activities Scale FATSCR MOBLSCR SCARESCR UESCR	Functional Activity Total Score Mobility Score Self-Care Score Upper Extremity Score	The total score, as well as subscale scores for mobility, self-care, and upper extremity function on an interview-administered functional disability measure will be recorded.

5.5 Exploratory Efficacy Variables

Exploratory Efficacy analysis variables for the study population in UX001-CL202 will include the parameters listed in Table 7. These Exploratory Efficacy analysis variables will be summarized for both Part I and Part II in this study to gain a better understanding of the 6 g/day SA-ER and 12 g/day SA-IR doses.

Table 7 Exploratory Efficacy Analysis Variables

Analysis Variable Name	Analysis Variable Description	Code List/ Variable Notes
Laboratory Studies: LBCAT=CHEM CK SA	Creatine Kinase (u/L) Sialic Acid	Biomarkers

Analysis Variable Name	Analysis Variable Description	Code List/ Variable Notes

6 STATISTICAL METHODOLOGY

6.1 Sample Size

Approximately 46 subjects may be enrolled in Part I of this open-label extension study. Sample size is limited to the number of subjects enrolled in the Phase 2 safety and efficacy study, UX001-CL201, who achieve at least 80% treatment compliance and study visit completion. As Part I of the study is intended to evaluate the long-term safety of 6g/day SA-ER in subjects with GNE Myopathy and ascertain the long-term effect of SA-ER treatment on muscle strength, mobility, and functional disability, the sample size is deemed reasonable to satisfy Part I study objectives.

An additional 10 subjects will be enrolled into Part II of the study. This subset of treatment naïve GNE Myopathy subjects will provide additional safety and efficacy information following treatment with SA-ER/SA-IR. Note that more than 10 planned subjects may be enrolled in this subset of treatment naïve GNE Myopathy subjects, as new subjects are identified at the study centers. These additional subjects will only add additional information and informative value to this treatment naïve GNE Myopathy population. No modifications of updates to the SAP are needed for additional subjects in this group.

The study design is open-label with all subjects receiving the same treatment. Therefore, the study is not powered to assess statistically significant comparisons. Instead, the sample size is intended to provide the maximum amount of long-term safety and efficacy data for the investigational product.

6.2 Randomization

This is an Open-Label Study where all subjects who roll over from study UX001-CL201 will receive 6g/day SA-ER in Part I and 12g/day SA-ER/SA-IR in Part II. Subjects enrolled into this study who are treatment naïve GNE Myopathy subjects will be included in Part II and receive 12g/day SA-ER/SA-IR. Since all subjects will receive the same treatment in Part II, randomization or blinding of study drug is not necessary. No randomization schedule or stratification strategy at baseline was developed for this study.

6.3 Analysis at 6-months (Part II)

An analysis will be conducted following 6 months of treatment with 12g/day SA-ER/SA-IR in Part II of the study. This analysis will be the primary analysis for the study for clinical efficacy information and initial safety information.

This analysis will be completed with the SAFETY, ITT, and TNP populations.

The independent DMC may review the safety information from the analysis to assess the impact on the safety of the participants or the ethics of the study. The DMC may also make other recommendations to Ultragenyx Pharmaceutical concerning continuation, termination or other modifications of the study based on their observations of the study at the analysis or other DMC scheduled review of study data.

Ultragenyx Pharmaceutical may also at its discretion complete additional examinations at additional time points for trends in efficacy and safety parameters after the analysis at 6-months (Part II) has been completed to monitor and assess the 12g/day SA-ER/SA-IR dose.

6.4 Final Analysis at end of Part II.

After all subjects have completed Part II dosing and follow-up termination visit on the 12g/day SA-ER/SA-IR dose at approximately 36 months, the database will be locked and final analyses will be completed.

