Part III of the study reduces the SA dose from 12g/day to 6g/day for subjects who did not show additional benefit at 12g/day at the interim analysis; however, treatment naïve subjects and a small subset of rollover subjects who showed a potential efficacy benefit will be invited to remain on the higher dose of 12g/day. Part III will assess the long-term safety and efficacy of 12g/day SA-ER/SA-IR treatment for the duration of the study for the subjects who stay on the higher dose in Part III and will provide additional information on the long-term safety and efficacy of 6g/day SA-ER for the remaining subjects.

Part IV was added to change the formulation from SA-IR to SA-ER. The SA-IR dose formulation has been removed based on data showing that by the 4th day of dosing in a nonclinical study conducted in dogs, AUC for free SA was similar between the immediate and extended release formulations. In addition, a review of population data for Month 12 of Part III in the current study confirmed that 12g/day SA-IR did not appear to provide any additional benefit compared with 6g/day SA-ER, although some individual patients may have improved. Therefore, no further SA-IR will be administered after the initiation of Part IV; patients currently on 12g/day may continue receiving the 12g/day dose, if desired, by taking SA-ER.

Evaluations of safety, changes in clinical endpoints such as muscle strength, mobility, and function, and changes in exploratory serum biomarkers will be performed according to the Schedule of Events specific to each phase of the study (Table 2.1 and Table 2.2). A Termination Visit will be conducted 4 weeks after subjects receive their last dose of study drug (last dose of study drug received at Month 36). For subjects who are eligible and choose to participate in the UX001-CL302 open-label extension study, the Month 36 Visit is considered the end of study visit and the Termination Visit is not required. Any subject who discontinues the current study early or is ineligible or decides not to participate in the UX001-CL302 extension study is required to have a Termination Visit 4 weeks after their last dose of study drug, as per Schedule of Events. Efficacy data analyses will be conducted at the end of the 36-month Treatment Period, although interim analyses may be performed at the discretion of Ultragenyx.

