following approximately 12 weeks of treatment with 6g/day SA-ER and continue on to Part II of the study by crossing over to an increased daily SA dose of 12g/day. Since Part II of the study will be the first time GNE Myopathy subjects will be treated with the SA-ER/SA-IR investigational product, approximately 10 GNE Myopathy subjects will be enrolled to assess long-term safety and clinical efficacy of SA-ER/SA-IR in a treatment naïve population.

An interim analysis was conducted after 6 months of treatment with SA-ER/SA-IR; the results of this interim analysis have led to the establishment of Part III of the study. Part III will provide long-term safety and efficacy data on both 6 and 12g/day SA. This change is based on a review of individual subject data for the rollover subjects from the parent study UX001-CL201. The data analysis suggests that a small subset of subjects received an added benefit from the higher dose (defined as at least a 15% increase in either the UEC or LEC). The rollover subjects who met these criteria, along with the ongoing naïve subjects, had the option to remain on the 12g/day dose for the remainder of the study.

Part IV was added to change the formulation from SA-IR to SA-ER. The SA-IR dose formulation has been removed based on data showing that by the 4th day of dosing in a nonclinical study conducted in dogs, AUC for free SA was similar between the immediate and extended release formulations. In addition, a review of population data for Month 12 of Part III in the current study confirmed that 12g/day SA-IR did not appear to provide any additional benefit compared with 6g/day SA-ER, although some individual patients may have improved. Therefore, no further SA-IR will be administered after the initiation of Part IV; patients currently on 12g/day may continue receiving the 12g/day dose, if desired, by taking SA-ER.

Patients who elect to decrease from 12 g/day to 6 g/day may be allowed to do so upon Sponsor approval.

The 36-month treatment duration is intended to evaluate the long-term safety and efficacy of SA. While the lack of a control group may introduce difficulties in discerning natural disease progression from treatment effectiveness, due to the progressive debilitating nature of the disease, a placebo-controlled study of this duration is not feasible

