1 INTRODUCTION

This document presents a statistical analysis plan (SAP) for Ultragenyx Pharmaceutical, Inc. Protocol UX001-CL202 (*An Open-label Phase 2 Extension Study to Evaluate the Long Term Safety and Efficacy of Sialic Acid-Extended Release (SA-ER) Tablets and Sialic Acid-Immediate Release (SA-IR) Capsules in Patients with GNE Myopathy or Hereditary Inclusion Body Myopathy*).

Reference materials for this statistical plan include the Protocol UX001-CL202 (Original: 01 March 2013, Amendment #1: 02 October 2013), UX001-CL202 Case Report Forms (24 July 2013), feeder study Protocol UX001-CL201 and the SAP for UX001-CL201 (05 November 2013: Week 48 Analysis). Study UX001-CL202 is an Open-Label extension study and treatment is not blinded. Subjects completing 48-week in study UX001-CL201 are eligible to continue treatment under this open-label extension protocol testing an increased dose of SA. Additional GNE Myopathy subjects will be enrolled to assess the safety and efficacy of SA-ER/SA-IR in a treatment naïve population. Ultragenyx Pharmaceutical is conducting UX001-CL202 in two parts:

- Part I of the study will provide additional information on the long-term safety and efficacy of 6g/day SA ER;
- Part II of the study will assess the safety and efficacy of 1.5 g of SA-ER / 1.5 g of SA-IR treatment 4 times per day (12g/day SA-ER/SA-IR total dose) for 6 months. If reasonable efficacy and safety are demonstrated at the interim analysis at 6 months post initiation of part II, the subjects may continue therapy for up to 36 months.

The statistical plan described hereafter is an *a priori* plan. The SAP will be finalized and approved prior to completing inferential or descriptive analyses of data pertaining Ultragenyx Pharmaceutical, Inc. Protocol UX001-CL202. Statistical Analysis programming may occur as study data accumulate in order to have analysis programs ready at the time the study finishes. For the reasons stated herein the conduct of the study in the field is considered to be independent of any study outcome that might materialize upon enactment of the currently proposed statistical analysis plan.

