6.5.1 Changes in Analysis in Comparison to Study Protocol

The analyses described in this analysis plan are consistent with the intended analyses described in the study protocol. In addition results from the UX001-CL201 study, both the Week 24 and Week 48 analyses, will be utilized as baseline information to explore and compare the various dosing combinations and trends in efficacy parameters, between the UX001-CL201 randomized feeder study and the UX001-CL202 extension study.

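### The supplied SAP stops at protocol Amendment 1, so its post-Month-6 groups and its final-analysis trigger do not fit Parts III and IV; the Month 6 comparisons are unaffected by design

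*SAP*

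**What the plan says.** **SAP**
- Section 1: "Reference materials for this statistical plan include the Protocol UX001-CL202 (Original: 01 March 2013, Amendment #1: 02 October 2013". It describes two parts. Section 6.5.1 adds: "The analyses described in this analysis plan are consistent with the intended analyses described in the study protocol".
- Section 3 has every subject on 12 g/day SA-ER/SA-IR throughout a 36-month Part II. Section 5.1 says "All subjects participating in Part II of this study will receive 12g/day SA-ER/SA-IR" and section 6.2 says that "all subjects who roll over from study UX001-CL201 will receive 6g/day SA-ER in Part I and 12g/day SA-ER/SA-IR in Part II".
- Sections 6.7.5, 6.7.6 and 6.7.11 summarise one 12 g/day SA-ER/SA-IR group at each time point; 6.7.6 lists the months up to 36. Sections 6.7.7 and 6.7.12 do the same within Part II.
- Section 6.10.1 has two adverse-event columns, 6 g/day SA-ER and 12 g/day SA-ER/SA-IR. Sections 6.6.1, 6.6.4 and 6.10.5 tie 6 g/day to Part I.
- Section 6.4 locks the database "After all subjects have completed Part II dosing and follow-up termination visit on the 12g/day SA-ER/SA-IR dose at approximately 36 months".

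**Protocol**
- Section 7.1: "Part III of the study reduces the SA dose from 12g/day to 6g/day for subjects who did not show additional benefit at 12g/day". Treatment-naïve subjects and a small subset of rollover subjects may stay on 12 g/day. Section 7.2 gives the criterion for added benefit, "defined as at least a 15% increase in either the UEC or LEC", and allows elective reduction with sponsor approval.
- Section 7.1, on Part IV: "no further SA-IR will be administered after the initiation of Part IV". Subjects on 12 g/day may continue it as SA-ER.
- Section 7.1 waives the Termination Visit for subjects who enter UX001-CL302.
- The synopsis and section 7.6.1.1 leave the Part III and IV analyses to the SAP. Section 7.6.1.1 also names a treatment difference at Month 36 as the final treatment effect, without saying which groups are compared.

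**The concern.** The SAP's treatment labels describe a study in which dose and formulation stay constant after Part II begins. The protocol now changes the dose for many subjects and the formulation for all who remain on 12 g/day. The timing of each change follows IRB/EC approval, not a study month (protocol Table 2.2, footnote b). If the SAP is followed as it stands, the long-term descriptive efficacy results cannot be read by dose or formulation. The safety objective for 6 and 12 g/day in Parts III and IV (protocol section 6) is only partly served. The final analysis also has no trigger that can be reached.

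The Month 36 treatment difference is a related gap. With no groups defined, an analyst might fill it with current dose. Among rollover subjects, current dose depends on each subject's own earlier change in strength.

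**Working it through.** There is no power or sample-size figure to reproduce: both documents say the study is not powered for comparisons. The check sets the texts side by side and then illustrates the size.

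**1. Where later visits go.** SAP section 4 analyses both the Safety and the ITT populations according to treatment received.
- A visit on 6 g/day after step-down, or on 12 g/day SA-ER alone, therefore does not belong to a 12 g/day SA-ER/SA-IR efficacy group and drops out. If the as-treated rule is not applied, the visit stays in under the wrong label.
- SAP section 6.5 keeps data outside the plan in listings only.
- The 6 g/day adverse-event column can take step-down events. The disposition, medication and falls tables have no place for post-step-down data.
- 12 g/day SA-ER alone has no group in any table.

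**2. The lock condition in SAP 6.4.** It fails on three counts: dose (some subjects move to 6 g/day), formulation (SA-IR is withdrawn), and the termination visit (waived for UX001-CL302 entrants).

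**3. The planned tables.** Tables 15 to 506 number 506 − 15 + 1 = 492, or 492 / 12 = 41 endpoints with 12 tables each. One of each 12 is a summary and 11 are comparisons: 41 × 11 = 451. All 451 carry Table 8 names, and every Table 8 comparison ends at Week 24 of 12 g/day. No table is labelled Part III, Part IV or Month 36.

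**4. Illustration of size.** Planned numbers from the documents: about 46 rollover and 10 naïve subjects, 56 in all. Dynamometry visits fall at Months 12, 18, 24, 30 and 36, giving 56 × 5 = 280 subject-visits. Assumptions, none from the documents:
- no dropout, and all naïve subjects stay on 12 g/day;
- k = 2 to 12 rollover subjects stay on 12 g/day;
- v = 3 to 5 of the visits are on 6 g/day for those who step down;
- w = 1 to 3 of the visits fall in Part IV.

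Share on 6 g/day = (46 − k)v / 280:
- k = 12, v = 3: 34 × 3 / 280 = 102/280 = 36%
- k = 2, v = 5: 44 × 5 / 280 = 220/280 = 79%

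Share not on 12 g/day SA-ER/SA-IR = [(46 − k)v + (k + 10)w] / 280:
- k = 12, v = 3, w = 1: (102 + 22)/280 = 124/280 = 44%
- k = 2, v = 5, w = 3: (220 + 36)/280 = 256/280 = 91%

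**5. Timing.** Part II was introduced by Amendment 1 (02 October 2013), so this is taken as the earliest start.
- By Amendment 2 (17 December 2014) no subject could be past Month 14.5 of Part II; by Amendment 3 (07 October 2015), none past Month 24.1.
- Some Month 12 visits may therefore precede the step-down.
- The earliest nominal Month 36 visit is 02 October 2016. Subtracting the 14-day visit window and the 5-week transition gives 14 August 2016, which is 312 days or about 10.2 months after Amendment 3. If every site had approval by then, no Month 36 visit would be on 12 g/day SA-ER/SA-IR. The approval dates are not given.

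**The case against.** The strongest reply is that this is a question of document version. The SAP matches the protocol version it names, so its consistency statement was not wrong against that version, and a later SAP may exist. That stands. A reader might infer that the sponsor has no plan for Parts III and IV; the documents show only that the supplied SAP has none.

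Four other stronger readings also go too far.
- **That all 6 g/day visits are reported as 12 g/day.** The as-treated rule also covers the ITT population, so omission is the main effect. SAP 6.5 tabulates by treatment, allows extra categories within a treatment and lists all data. This softens the problem but creates no new groups.
- **That every SAP section assumes 12 g/day to Month 36.** Sections 5.1 and 6.2 speak only of Part II, and section 1 makes continuation past 6 months conditional. The 36-month assumption sits in sections 3 and 6.4. Sections 6.7.7 and 6.7.12 reach Month 36 only if Part II is read as 36 months.
- **That the protocol plans a biased Month 36 comparison.** Protocol 7.6 calls itself a guide and refers detail to the SAP. Neither document proposes a contrast by current dose, so selection on earlier response would arise only if someone chose one. The comparison of 6 g and 3 g starters with projected placebo covers muscle strength only and is not linked to the Month 36 model.
- **That the Month 6 primary analysis is compromised.** Part III was set up from the Month 6 results, so those comparisons precede the dose split by design. One reservation remains: the trigger was a majority of subjects at Month 6 and enrolment dates are not given, so an effect on a late-enrolled naïve subject cannot be fully excluded.

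**Conclusion.** The point holds for the supplied SAP and should be fixed before final lock. Its later efficacy groups, several safety groups and its lock condition are wrong for the current protocol, which is more than a lack of detail. The textual mismatch needs no assumptions.

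The size does need them. The documents say only that a small subset of rollover subjects stayed on 12 g/day, so the 36% to 79% and 44% to 91% ranges are illustrations, not estimates. They cover dynamometry only. That no one remains on the labelled regimen at Month 36 is likewise conditional on approval dates.

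The Month 36 treatment difference is undefined wording that needs a definition. The bias of a current-dose contrast cannot be sized from the documents, and no figure is offered.

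**What to change.** 1. **Groups and sequences.** Amend SAP Table 3 and sections 6.4, 6.6, 6.7 and 6.10.
   - Assign each visit to the dose and formulation taken on that date, and each adverse event to those at onset, from dosing records.
   - Define groups for 12 g/day SA-ER/SA-IR, 12 g/day SA-ER, Part I 6 g/day and post-step-down 6 g/day. State in each table whether the two 6 g/day sets are pooled.
   - Define sequences separately for rollover and naïve subjects, each with a stay-on-12 g and a step-down path, the latter including elective step-down.
   - Keep subjects with a temporary tolerability step-down in their assigned sequence, and flag those periods.
2. **Lock trigger.** Replace the SAP 6.4 condition with: all subjects have completed Month 36 or terminated early, plus the Termination Visit where the protocol requires it.
3. **Month 36 estimate.** In the SAP, and in protocol 7.6.1.1 at its next amendment, replace the undefined treatment difference with within-sequence change and 95% confidence intervals. Keep the projected-placebo comparison as a separate analysis. Label any 6-versus-12 g/day display after Part III as descriptive and response-selected.
4. **Length of Part II.** Protocol 7.1 gives a 36-month Part II with all subjects on 12 g/day and then describes the Part III reduction; protocol 7.2 gives Part II up to 12 months. These passages must be reconciled so that each sequence has defined start and end points. This does not involve choosing a dose.

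The cost is a SAP amendment, programming and protocol wording, with no new data and no change to dosing. The trial gives up a Month 36 between-dose estimate that its design cannot support.
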